### **9 DATA AND STUDY MANAGEMENT**

#### **9.1 Data Monitoring & Interim Analyses**

A DMC will be convened and meet regularly to discuss study progress, recruitment targets and future planning. If a trial stopping rule was triggered a DMC meeting would be convened to review the TMG's decision to stop/continue the trial.

Quality control checking and introduction of improvement procedures for data analysis will be ongoing throughout data collection. The study uses the continual reassessment method to assess the dose-toxicity response. There is no formal plan for interim data analysis of secondary outcomes before the completion of the study, however data will be continuously monitored to determine whether data collection should continue as planned, or be targeted towards a particular demographic or methadone dose to increase precision in secondary outcomes.

## **9.2 Direct Access to Source Data & Documents**

In the event of an audit or study related monitoring procedure, where source documents and data has to be reviewed, the chief investigator will permit study related monitoring, which will require access to source data or documents.

During the study, it will only be the Chief Investigator, the co-investigators, as well as the rest of the research team involved in the study, who will have access to data produced by the study.

## **9.3 Data handling and record keeping**

This study and its staff will be compliant with the Data Protection Act and GDPR with regards to the collection, storage, processing and disclosure of personal information. It is under the Chief Investigator's responsibility to be up to date and comply with the requirements of the law and relevant guidelines relating to security and confidentiality of patient or other personal data, including the need to register, when necessary, with the appropriate Data Protection Officer.

The study team will complete a Data protection impact assessment (DPIA) according to data protection legislation to identify how the study will process and store data and to identify and minimise data protection risks.

### **9.3.1 Personal data**

Personal contact details are required for communication with the subjects participating in the study. This information is held solely for communication between the researchers and participants.

Information held on NHS computers is solely for the purpose of hospital booking and routine sample collection and analysis (e.g. for medical screening). This information is password protected in a similar manner to that of other hospital patients. Access to additional patient records is explicitly requested from participants and this is made clear in the Information/Consent forms.

Each participant will be identified by a unique code number that will be used throughout the duration of the study. Participant names, addresses, and other contact details will be written in the clinical screening portion of the paper-based CRF for identification and contact purposes. The clinical screening CRFs will be regarded as confidential, and kept in locked filing cabinets in Imperial College. The contact details will then be removed from the CRF and into participant notes for storage.

Only the CI, and selected study team members will have access to anonymised codes and their link to personal ID. This will be kept locked in a file on site and electronically on secure servers accessed by research team members only (password protected).

### **9.3.2 Study data management**

All data will be collected in a pseudonymised and coded manner and stored within paper-based CRFs and/or via electronic data capture (EDC) within purpose built secure-access online databases; OpenClinica and REDCap, or saved electronically on secure University (Imperial College) computer systems and facilities. This will ensure

the safe acquisition, storage and transmission of data. University computers and servers are all password protected and study data can only be accessed by the researchers involved in the study.

Quality control will be conducted according to ICTU, OpenClinica, REDCap or FORWARDS study SOPs, as appropriate.

### **9.3.3 OpenClinica**

The electronic data capture (EDC) system for collecting and entering data is OpenClinica on an all-in-one platform. It is fully validated and compliant with 21 Code of Federal Regulations (CFR) Part 11 - Electronic Records; Electronic Signatures. The EDC system is also ICH-GCP and ISO9001 compliant.

The Imperial College Clinical Trials Unit (ICTU) will be responsible for study control; from eCRF design to study close-out; database build and system validation while OpenClinica Cloud will be responsible for hosting the data. The trial specific OpenClinica system is built from requirements defined by the Chief Investigator, Trial Statistician and Study Manager and approved by the Chief Investigator. eCRF design documents and all approvals will be filed in the Trial Master File (TMF). The OpenClinica system will be built with data validation, automatic queries, alerts and edit checks as defined in the study requirements.

The system is capable of real-time data entry for rapid access such that the Dose Setting Committee can make timely updates to the adaptive Bayesian model after (at most) every baclofen group of 3 participants.

Access permissions to OpenClinica will be managed by ICTU according to the trial requirements and SOPs. Data entry will be managed according to ICTU and FORWARDS SOPs.

### **9.3.4 REDCap**

Exploratory outcomes will be captured using REDCap (Research Electronic Data Capture) tools hosted at Imperial College London (PA Harris, 2019, 2009). REDCap is a secure, web-based software platform designed to support online or offline data capture for clinical research studies, providing 1) an intuitive interface for validated data capture; 2) audit trails for tracking data manipulation and export procedures; 3) automated export procedures for seamless data downloads to common statistical packages; and 4) procedures for data integration and interoperability with external sources.

REDCap can be used to capture a variety of types of data including 21 CFR Part 11, FISMA and HIPAA compliant environment.

### **9.3.5 Custodian of the Data**

The CI, [name], will be custodian of the data.

### **9.3.6 Format of Records**

Personal data and raw data formats will be stored in patient hospital notes, paper-based CRFs or on password protected computer systems within the study sites, as appropriate.

Screening data will be pseudonymised where possible, and stored in paper-based or eCRFs, as appropriate.

Study data will be pseudonymised and stored in paper-based or eCRFs, as appropriate.

### **9.3.7 Duration & Location of stored data**

Primary research data / records will be retained in their original form for a minimum of 10 years after the study has been completed.

Location of data: Data will be stored within paper-based CRFs according to local security procedures, electronically on secure University (Imperial College) computer systems and facilities or within purpose built secure-access online databases, OpenClinica and Redcap, as detailed above.

## **9.4 Training and User Support**

All staff employed on the grant and all Investigators will be trained in:

- GCP
- Use of the assessment tools
- Study standard operating procedures
- Use of Study databases (OpenClinica & REDCap)

All staff working directly with participants will have a CRB check, a License to attend (or equivalent) for the ICRF, and an honorary contract (or research passport) with Central and North West London (CNWL) NHS trust.

# **10 ADVERSE EVENT REPORTING**

## **10.1 Adverse Events and Adverse Reactions**

### **10.1.1 Definitions**

**Adverse Event (AE):** any untoward medical occurrence in a patient or clinical trial subject administered a medicinal product and which does not necessarily have a causal relationship with this treatment. *An AE can therefore be any unfavourable and unintended sign (including an abnormal laboratory finding), symptom, or disease temporally associated with the use of an investigational medicinal product (IMP), whether or not considered related to the IMP.*

**Adverse Reaction (AR):** all untoward and unintended responses to an IMP related to any dose administered. *All AEs judged by either the reporting investigator or the sponsor as having reasonable causal relationship to a medicinal product qualify as adverse reactions. The expression reasonable causal relationship means to convey in general that there is evidence or argument to suggest a causal relationship.*

**Unexpected Adverse Reaction:** an AR, the nature or severity of which is not listed in the reference safety information (RSI) e.g. list of expected medical events within investigator's brochure for an unapproved investigational product or section 4.8 of the summary of product characteristics (SmPC) for an authorised product. *When the outcome occurs this adverse reaction should be considered as unexpected. Side effects*

*documented in the SmPC which occur in a more severe form than anticipated are also considered to be unexpected.*

**Serious Adverse Event (SAE) or Serious Adverse Reaction:** any untoward medical occurrence or effect that at any dose:

- **Results in death.**
- **Is life-threatening** – refers to an event in which the subject was at risk of death at the time of the event; it does not refer to an event which hypothetically might have caused death if it were more severe.
- **Requires hospitalisation, or prolongation of existing inpatients' hospitalisation.**
- **Results in persistent or significant disability or incapacity.**
- **Is a congenital anomaly or birth defect.**

Medical judgement should be exercised in deciding whether an AE/AR is serious in other situations. Important AE/ARs that are not immediately life-threatening or do not result in death or hospitalisation but may jeopardise the subject or may require intervention to prevent one of the other outcomes listed in the definition above, should also be considered serious.

**Suspected Unexpected Serious Adverse Reaction (SUSAR):** any suspected adverse reaction related to an IMP that is both unexpected and serious.

#### **10.1.2 CAUSALITY**

Most adverse events and adverse drug reactions that occur in this study, whether they are serious or not, will be expected treatment-related toxicities due to the drugs used in this study. The assignment of the causality should be made by the investigator responsible for the care of the participant using the definitions in the table below.

If any doubt about the causality exists the local investigator should inform the study coordination centre who will notify the Chief Investigators. The pharmaceutical companies and/or other clinicians may be asked to advise in some cases.

In the case of discrepant views on causality between the investigator and others, all parties will discuss the case. In the event that no agreement is made, the MHRA will be informed of both points of view.

Relationship	Description
Unrelated	There is no evidence of any causal relationship
Unlikely	There is little evidence to suggest there is a causal relationship (e.g. the event did not occur within a reasonable time after administration of the trial medication). There is another reasonable explanation for the event (e.g. the participant's clinical condition, other concomitant treatment).
Possible	There is some evidence to suggest a causal relationship (e.g. because the event occurs within a reasonable time after administration of the trial medication). However, the influence of other factors may have contributed to the event (e.g. the participant's clinical condition, other concomitant treatments).

Probable	There is evidence to suggest a causal relationship and the influence of other factors is unlikely.
Definitely	There is clear evidence to suggest a causal relationship and other possible contributing factors can be ruled out.
Not assessable	There is insufficient or incomplete evidence to make a clinical judgement of the causal relationship.

### **10.1.3 REPORTING PROCEDURES**

All adverse events should be reported. Depending on the nature of the event the reporting procedures below should be followed. Any questions concerning adverse event reporting should be directed to the study coordination centre in the first instance. A flowchart is given below to aid in the reporting procedures.

### **10.1.4 NON SERIOUS AR/AES**

All such toxicities, whether expected or not, should be recorded in the toxicity section of the relevant case report form and sent to the study coordination centre within one month of the form being due.

### **10.1.5 SERIOUS AR/AES**

Fatal or life threatening SAEs and SUSARs should be reported on the day that the local site is aware of the event. The SAE form asks for nature of event, date of onset, severity, corrective therapies given, outcome and causality (i.e. unrelated, unlikely, possible, probably, definitely). The responsible investigator should sign the causality of the event. Additional information should be sent within 5 days if the reaction has not resolved at the time of reporting.

#### **SAEs**

An SAE form should be completed and sent to the study coordination centre for all SAEs within 24 hours. OpenClinica software facilitates notification of the SAE form via email. However, relapse and death or hospitalization due to substance use disorder that cannot reasonably be attributed to study medication, and hospitalisations for elective treatment of a pre-existing condition do not need reporting as SAEs.

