### **5.7.4 Emergency Unblinding Procedure**

This is single-blind- study clinicians and researchers will be aware of the drug allocation that was recommended by the adaptive trial algorithm and this allocation will be stored within the OpenClinica Database and accessible to the research team.

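### Deaths and hospitalisations put down to substance use and judged not attributable to study medication need no SAE form, so causality is decided before reporting, by investigators who know the allocation

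*Combined protocol and SAP*

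**What the plan says.** Section 10.1.1 defines an adverse event as one "which does not necessarily have a causal relationship with this treatment". It defines a serious event as "any untoward medical occurrence or effect that at any dose" leads to one of a list of outcomes, death and hospitalisation among them. Neither definition depends on cause.

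The reporting rules start from the same position. Section 10.1.3 says "All adverse events should be reported". Section 10.1.5 says "Fatal or life threatening SAEs and SUSARs should be reported on the day that the local site is aware of the event", and lists causality, from unrelated to definite, among the items on the SAE form. Under SAEs it adds "An SAE form should be completed and sent to the study coordination centre for all SAEs within 24 hours".

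The next sentence but one makes an exception. It says that "relapse and death or hospitalization due to substance use disorder that cannot reasonably be attributed to study medication", together with elective admissions for existing conditions, "do not need reporting as SAEs".

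Section 10.1.2 gives the causality assignment to the investigator caring for the participant. Section 5.7.4 says that "study clinicians and researchers will be aware of the drug allocation".

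**The concern.** Participants have severe opioid use disorder, take methadone, and receive a single dose of a second CNS depressant. Whether the two can be combined safely is the trial's question. If someone is admitted or dies with an overdose picture on the evening after dosing, two explanations compete: illicit use on top of the prescription, or the baclofen-methadone combination. The exemption asks the local investigator to choose between them before any form exists. If the choice is substance use, nothing in the protocol requires the reasoning to be written down or seen by anyone else.

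At stake is the completeness of serious-event reporting to the coordination centre and, through it, to the DMC. The trial is small, and its safety findings are meant to inform the efficacy study that follows.

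**Working it through.** The protocol gives no figure on this point, so the check sets the sections against each other.

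1. **Definition against reporting.** Section 10.1.1 decides seriousness by outcome. The exemption in Section 10.1.5 leaves that definition alone. It removes the reporting duty for a subset chosen by cause. The tension is therefore with the reporting rules in Sections 10.1.3 and 10.1.5, which otherwise ask for a report first and a causality grade on it.

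2. **Order of the judgement.** Normal route: event, form, causality recorded, others can review and disagree. Exempted route: event, causality judged locally, no form. Section 10.1.1 lets either the investigator or the sponsor classify an event as an adverse reaction, and Section 10.1.2 has a procedure for discrepant views. Both need someone other than the investigator to know of the event.

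3. **Where an exempted event is recorded.** Section 10.1.3 refers to the procedures that follow it. Section 10.1.4 gives a case-report-form route for non-serious events only. Section 10.1.5 covers serious events and then exempts this one. No section says where an exempted death or hospitalisation is written down.

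4. **How clear the attribution test is.** The exemption speaks of study medication without saying whether an interaction with methadone counts. Methadone is the participant's own prescription (Section 5.4.2). In the Section 10.1.2 table, *Unlikely* cites the participant's condition or other concomitant treatment as an alternative explanation. *Possible* allows for the same factors but turns on timing. An overdose soon after dosing can be argued into either category.

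5. **What else would catch the event.** The DLT criteria in Section 3.4.2 use intervention level, NEWS2, respiratory measures, GCS and QTc, with no causality filter. Section 3.4.6 ends them at 5 hours, except intervention level, which runs to the last follow-up call. After discharge no staff are present to score that level directly. Section 5.8.7 stops adverse event recording after the call. From discharge to the call, adverse event reporting is the main safeguard.

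6. **Whether drug is still present then.** Section 5.4.3 gives a half-life of about 3 hours and a peak at 88 to 102 minutes. Assuming simple first-order decline, the fraction of peak concentration left at 300 minutes is 0.5^((300 − 88)/180) = 0.44 to 0.5^((300 − 102)/180) = 0.47. Counting from dosing instead gives 0.5^(5/3) = 0.31. Section 5.4.2 puts methadone's half-life at about 24 hours. Section 7.1.1 reports mild next-day effects in one healthy volunteer after 90 mg. Both drugs are therefore still present in the exposed window.

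**The case against.** The best defence is that the exemption carries its own safeguard: it applies only when the event cannot reasonably be attributed to study medication. An overdose hours after dosing would normally meet the timing test for *Possible* in Section 10.1.2 and so remain reportable. Section 10.1.2 also sends any doubt about causality to the coordination centre. On this view, harm needs an investigator to misapply the protocol. Much of this stands, and it makes the problem small. It does not remove it, because the safeguard works only if the investigator feels doubt, and no record would show that the question was considered.

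Several stronger readings are tempting, and the documents do not support them.

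- A reader might infer a blanket exemption for all substance-use deaths and admissions. The attribution qualifier rules that out.
- A reader might infer that the SAE definition is contradicted. The text is an explicit exception to reporting and leaves the definition as it is.
- A reader might infer that the trial would hide the event it exists to detect. The primary outcome does not use SAE reports. Participants are supervised for 5 hours and leave only with the study physician's approval (Section 5.4.15). The next-day call asks about adverse events (Section 5.5).
- A reader might infer that knowing the allocation biases the judgement towards substance use. It could as easily push the other way. The documents give no direction.
- A reader might measure the problem by what one event does to the summary. With the maximum of 48 on baclofen, no events gives a one-sided 95% upper limit of 1 − 0.05^(1/48) = 6.1%, and one event gives 2.1% (exact 95% interval 0.05% to 11.1%). The arithmetic is right, but it holds for any 0/48 or 1/48, pools all doses, and says nothing about how often the exemption would be misused.

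**Conclusion.** The point holds in a limited form. The exemption puts a causality judgement, made by investigators who know the allocation, ahead of a form that already records causality. It also leaves an exempted death or hospitalisation with no stated place to be recorded. The exposed period is chiefly discharge at about 5 hours to the call the next day, for up to 64 participants (48 baclofen, 16 placebo). Very few such events should be expected, possibly none, and no rate can be derived from the documents.

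The conclusion rests on two assumptions: that an overdose-type event in this window could plausibly be judged substance-use related, and that no other document, such as a site SOP, supplies a recording route. It is worth correcting because the remedy is almost free and protects the period in which little else captures events.

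**What to change.** Reconcile the exemption in Section 10.1.5 with Sections 10.1.1, 10.1.3 and 10.1.4 and with the same-day rule for fatal events. Wording to this effect would do:

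*Every death and every unplanned hospitalisation between dosing and the last follow-up call is reported on an SAE form, whatever its presumed cause. The investigator records causality on the form, considering baclofen both alone and in combination with methadone. Relapse without hospitalisation, and elective admission for a pre-existing condition, do not require an SAE form.*

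The exemption stays where it is useful, and no aspect of participants' care changes. The cost is a short protocol edit and at most a few additional SAE forms.

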#### **SUSARs**

In the case of suspected unexpected serious adverse reactions, the staff at the site should:

Complete the SAE case report form & send it immediately (within 24 hours,), signed and dated to the study coordination centre together with relevant treatment forms and anonymised copies of all relevant investigations.

**Or**

[figure not shown]
Contact the study coordination centre by phone and then send the completed SAE form to the study coordination centre within the following 24 hours as above.

The study coordination centre will notify the MHRA, REC and the Sponsor of all SUSARs occurring during the study according to the following timelines; fatal and life-

threatening within 7 days of notification and non-life threatening within 15 days. All investigators will be informed of all SUSARs occurring throughout the study.

Local investigators should report any SUSARs and /or SAEs as required by their Local Research Ethics Committee and/or Research & Development Office.

## 11 REGULATORY ISSUES

### 11.1 CTA

This study has Clinical Trials Authorisation from the UK Competent Authority; MHRA.

**EudraCT number:** 2021-002556-36

## **11.2 ETHICS APPROVAL**

The Study Coordination Centre has obtained approval from the West of Scotland REC 1 Research Ethics Committee (REC) and Health Regulator Authority (HRA). The study must also receive confirmation of capacity and capability from each participating NHS Trust before accepting participants into the study or any research activity is carried out. The study will be conducted in accordance with the recommendations for physicians involved in research on human subjects adopted by the 18th World Medical Assembly, Helsinki 1964 and later revisions.

